## **Data Analysis**

Measurement repeatability between two measurements will be assessed with a reliability parameter, which is also known as an intraclass correlation (ICC), as it equals the correlation between any two measurements made on the same subject. The difference between pairs of measurements will be plotted against their mean in a Bland-Altman plot. The average difference between measurements will be calculated as well as the 95% limits of agreement (LOA).

## **Study End Points**

Study end points (measures that will be considered as success):

1. The examination using CM is safe, does not cause significant discomfort and is capable of production of expected measurement results.
2. The CM elasticity measurements have intraoperator ICC of 0.90 or above; 95% LOA is within  $\pm 15\%$ .
3. The CM cervix length measurements have intraoperator ICC of 0.93 or above; 95% LOA is within  $\pm 10\%$ .

## **Protection of Human Subjects**

### Human Subjects Involvement, Characteristics and Design

Adult non-pregnant women scheduled for a regular gynecological examination at Princeton Urogynecology (Princeton, NJ) will be considered eligible for enrollment into the study with Cervix Monitor (CM). Conditions precluding patients from participation are listed in the study exclusion criteria below. This study with non-pregnant women is conducted to assess potential risks to pregnant women and fetuses as required by Code of Federal Regulations, Title 45, §46.204(a). This study with non-pregnant women will be conducted before initiation the study with pregnant women.

The highest priority will be given to consideration of examination safety with CM probe, disturbing the cervix tissue during pregnancy and potential risk of premature delivery, infection or miscarriage. Clinical study coordinators will maintain a log as to any concerns, complications, or suggested improvements in using the CM probe. After the CM examination a questionnaire will be presented to patients to assess their comfort and pain concerns relative to the procedure. All clinical investigators will have their CV on file with the local IRB and complete training and certification in Protecting Human Research Participant. Explanation of how data from the sites will be obtained, managed, and protected is presented in Data and Safety Monitoring Plan section (see below).

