### Subjects

The study will involve 10 non-pregnant, 2 CM measurements per subject. Adult non-pregnant pre-menopausal women scheduled for a regular gynecological examination at Princeton Urogynecology (Princeton, NJ) will be considered eligible for enrollment into the study. Each patient will first be studied with the existing clinical means and then with the CM. A clinical research assistant will maintain a log as to any concerns/complications with the CM.

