## Data Collection

Cervix tissue elasticity and length measurement data as well as patient age, weight, height and parity, patient questionnaire (CM scan comfort, pain).

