## **Methods and Procedures**

The examination procedure will comprise the steps of:

1. Inserting the speculum into the vagina to provide appropriate visualization and access to the cervix.
2. Performing CM measurements at 3, 6, 9, and 12 o'clock specifying the probe tip location on cervix on the touch screen display.
3. Review the measurement results (elasticity and length values) and repeat two measurements, one at the location with the lowest elasticity and one at the location with highest value.
4. Removing the probe and speculum from the vagina.

This CM examination procedure will be explored and further optimized based on the practical experience.

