### Source of Materials

Upon patient's consent, relevant clinical and demographical data will be collected. Specifically, obstetrical history, course of the previous current pregnancy(s), history of prior surgery and a connective tissue disorders (i.e. Ehlers-Danlos Syndrome, Benign Joint Hypermobility Disorder, etc.), race, age, height, weight, and parity will be documented.

Prior to taking the CM scan, standard obstetric external and internal vaginal examination will be performed by a clinical investigator. Attention to cervix softness, elasticity and any abnormalities

will be made and the results recorded to map the cervix surface. A 4-point grading system for cervix elasticity would be giving soft (0), or moderately soft (1), or moderately stiff (2), or stiff (3) elasticity scores to cervix. These subjective measurements would then be correlated with the CM data for agreement or discordance.

The CM examination will be performed as described above in Methods and Procedures section. The process is quick, non-invasive and should cause no additional discomfort to the patient as compared to a standard pelvic examination. All results will be recorded using an examination chart, which will be a part of the Case Report Form (CRF) specifically designed for the study. The chart will summarize all findings by all mean to characterize the cervix in terms of appearance and elasticity.

All necessary clinical and demographic data will be derived from existing records and de-identified. No additional clinical tests will be ordered to support this research. A specific clinical study number will be generated for each examination case so the link between the data and the patient will be created without revealing patient identity.

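### With no comfort or pain rating before the CM examination, a raised post-CM score cannot be cleanly attributed to the CM, and the stated expectation against a standard pelvic examination cannot be tested

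*Combined protocol and SAP*

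**What the plan says.** The order of examinations is fixed. Under Subjects: "Each patient will first be studied with the existing clinical means and then with the CM". Source of Materials says what comes first: "Prior to taking the CM scan, standard obstetric external and internal vaginal examination will be performed by a clinical investigator". Under Methods and Procedures, the CM examination then begins with a speculum: "Inserting the speculum into the vagina to provide appropriate visualization and access to the cervix". Probe measurements follow at four positions, with two repeats.

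One patient rating is described. Human Subjects Involvement, Characteristics and Design says: "After the CM examination a questionnaire will be presented to patients to assess their comfort and pain concerns relative to the procedure". The Data Collection list names its object: "patient questionnaire (CM scan comfort, pain". No rating before the CM, or between the two examinations, is described.

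Two statements bear on how the rating would be used. Study End Points, item 1, sets the success criterion: "The examination using CM is safe, does not cause significant discomfort and is capable of production of expected measurement results". Source of Materials gives an expectation, which is not an end point, that the CM process "should cause no additional discomfort to the patient as compared to a standard pelvic examination".

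**The concern.** Two examinations of the same anatomy follow each other in the same order in all 10 women, and only the second is followed by a rating. Discomfort left over from the first can be reported as discomfort from the second. End point 1 is worded causally ("does not cause significant discomfort"), so a raised score raises the question of what caused it, and the planned data contain nothing to answer that with. The comparative expectation in Source of Materials fares worse: one side of the comparison is not measured at all.

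The study is meant to inform the risk assessment that precedes work in pregnant women. A tolerability signal that cannot be traced to its source is a weak input to that step, whether the device is blamed for discomfort it did not cause or a real signal is explained away as left over from palpation.

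**Working it through.** The plan gives no discomfort rate, scale, cut-off or derivation of the sample size for this end point, so there is no figure to reproduce. The check sets the sections side by side and then illustrates the size under stated assumptions.

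**1. What each statement needs.**
- *End point 1, discomfort part:* an absolute judgement on the CM examination. It needs a post-CM rating, which is planned, and, if that rating is raised, some basis for attribution, which is not.
- *Expectation in Source of Materials:* a comparison with a standard pelvic examination. It needs a rating of both examinations. Only one is described.
- *Speculum:* it is the first step of the CM procedure, so discomfort from it belongs in the CM score. Only the earlier examination is a possible contaminant.

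**2. One woman.** Assume a 0–10 pain item (the plan names no scale). A post-CM score of 4 fits a score of 4 after the standard examination (4 − 4 = 0 added) and equally a score of 0 (4 − 0 = 4 added). The planned data do not separate these.

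**3. Ten women.** Let p be the proportion for whom the CM itself causes significant discomfort, and c the proportion of the rest who attribute earlier discomfort to it. Both are assumptions. The reported proportion is q = p + (1 − p)c, and P(at least 1 of 10 reports) = 1 − (1 − q)^10.

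| p | c | q | P(at least 1 of 10) |
|---|---|---|---|
| 0 | 0.10 | 0.10 | 1 − 0.9^10 = 65% |
| 0 | 0.20 | 0.20 | 1 − 0.8^10 = 89% |
| 0 | 0.30 | 0.30 | 1 − 0.7^10 = 97% |
| 0.10 | 0 | 0.10 | 1 − 0.9^10 = 65% |

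The first and last rows are the point. A harmless device with 10% misattribution and a device that causes discomfort in 10% of women give the same reported rate, and a post-CM rating alone cannot tell them apart.

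**4. A clean result.** In this model carry-over only adds reports, so 0 of 10 cannot be produced by carry-over. It stays interpretable, though imprecise: the exact (Clopper-Pearson) upper bound on the reported rate is 1 − 0.05^(1/10) = 25.9% (one-sided 95%), or 1 − 0.025^(1/10) = 30.8% (two-sided 95%).

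**The case against.** The strongest reply is that the end point does not need a comparison. It is absolute, Data Collection directs the questionnaire at the CM scan rather than the whole visit, and staff also keep a log of concerns and complications with the CM. All of this stands. Directing a question at the CM scan makes misattribution less likely but does not rule it out, and a staff log is not a patient-rated comparison. So the reply limits the point without removing it.

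Four stronger readings are tempting, and the documents do not support them:
- *That the discomfort part of end point 1 cannot be judged because of carry-over.* Low scores would support it; only raised scores are ambiguous.
- *That carry-over biases the result in both directions.* Additive carry-over raises scores. Adaptation after the first examination could lower them, but the documents give nothing on its size. A moderate score for a CM examination that was worse than palpation is not carry-over, and may be acceptable under an absolute criterion.
- *That one or two misattributed scores would change the verdict.* One woman is 10 percentage points of 10, but a changed verdict presupposes a decision rule, and none is stated.
- *That a woman is certainly asked only once.* This is the only questionnaire described, but the form is not shown.

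It is also fair to object that a baseline rating would not settle what counts as significant discomfort. The plan gives no scale, cut-off or permitted number of women, and Data Analysis covers only the ICC and Bland-Altman analyses of the measurements. That separate gap is the larger obstacle to judging this part of the end point, and the change proposed here does not close it.

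**Conclusion.** The point holds as a minor design weakness. With the fixed order and no rating described before the CM, a raised post-CM score cannot be cleanly attributed to the CM rather than to the examination before it, and the expectation of no added discomfort relative to a standard pelvic examination cannot be tested. Low scores in all 10 women would still support the absolute criterion.

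The size is not known from the documents. The 65% to 97% figures are scenarios for misattribution of 10% to 30% with a CM that causes no discomfort; they assume independent women and purely additive carry-over. The conclusion also assumes that the questionnaire described is the only one planned.

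**What to change.** In Human Subjects Involvement, Characteristics and Design, and in the Data Collection list, state that the same short comfort and pain items are given twice: after the standard examination and before the speculum and CM, and again directly after the CM examination.

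Keep the post-CM score as the basis for end point 1. Report each woman's change beside it, for all 10 women, to help attribute raised scores and to check the expectation in Source of Materials. Do not judge the end point on the change alone: a woman with high scores after both examinations would show no change and would pass, although the CM examination hurt. A separate item on probe contact is optional, because the speculum is part of the CM procedure.

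The cost is about a minute per visit and one CRF page, with no change to the examinations. Two limits remain. The first answer may anchor the second. And since the CM still always comes second, the change retains some order effect, so it aids attribution without proving cause.

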#### Potential Risks

Investigators do not expect any additional risks or side effects from the use of CM beyond those normally associated with standard manual palpation and transvaginal ultrasound, such as extremely rare possibility of physical damage of the vagina, cervix tissue and infection. Other risks include software/hardware malfunction, toxicity, allergic reaction, electrical shock and breach of confidentiality.

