#### Data and Safety Monitoring Plan

The Principal Investigator will be responsible for proper monitoring of the investigation and compliance with written monitoring procedures (§§ 812.46 and 812.25(e)); ensure that IRB approval is obtained (§812.42) and any reviewing IRB and FDA are promptly informed of significant new information about an investigation (§812.150); control distribution and disposition of investigational products (§812.43).

Clinical investigators perform the data safety monitoring function and are responsible for concurrent reporting of any adverse events that occur as a result of this study to the local approving IRB and to the Principal Investigator. All events will be categorized as to their degree of seriousness and relation to the use of the PTI. Principal Investigator will collect and analyze adverse effects, highlight its course and propose means to negate such effects.

ATI staff will monitor the study by auditing CRFs, verifying the consistency of raw CM data, and checking clinical protocol compliance. Communication with clinical investigators will be primarily in a form of phone and e-mail. In addition, ATI's representative will visit all participating clinical sites. Establishment Inspection Report (EIR), a detailed record of the inspection and findings, will be prepared after the visit. Also, such interactions will result in a clinical database that will be set to store all information obtained during the course of the study.

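### No active follow-up after the examination is visible, so delayed harms such as infection reach the study only through passive reporting before the examination is judged safe

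*Combined protocol and SAP*

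**What the plan says.** Assessing risk ahead of use in pregnancy is the first of the Study Objectives. The first item under Study End Points reads: "The examination using CM is safe, does not cause significant discomfort and is capable of production of expected measurement results". It gives no event definition and no time window. Recruitment and Informed Consent places the study in pregnant women after this risk assessment. Potential Risks names an "extremely rare possibility of physical damage of the vagina, cervix tissue and infection".

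The women's own reports are collected once. Human Subjects Involvement, Characteristics and Design states: "After the CM examination a questionnaire will be presented to patients to assess their comfort and pain concerns relative to the procedure". Data Collection lists the same item as "patient questionnaire (CM scan comfort, pain". The last step under Methods and Procedures is "Removing the probe and speculum from the vagina".

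There are also staff-side routes. The Subjects section says: "A clinical research assistant will maintain a log as to any concerns/complications with the CM". Human Subjects Involvement repeats this with a wider scope: "Clinical study coordinators will maintain a log as to any concerns, complications, or suggested improvements in using the CM probe". The Data and Safety Monitoring Plan adds: "Clinical investigators perform the data safety monitoring function and are responsible for concurrent reporting of any adverse events". It also requires each event to be categorised by seriousness and by relation to the device. None of these routes carries an end date, and none states that a woman is contacted once she has left.

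**The concern.** An infection would usually declare itself after the woman has gone home, and a questionnaire on comfort and pain is not designed to find it. The log and the adverse event reports act only on what someone brings to the study. A woman who is treated elsewhere, or who does not connect a symptom with the examination, is not asked. The sterile single-use shaft described in Protection Against Risks is prevention. It does not check whether prevention worked.

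At stake is what an event-free result would mean. The safety end point could be declared met because nothing was reported, although delayed harms were never sought, and that declaration would feed into the decision to examine pregnant women.

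**Working it through.** **1. Search for later contact.** Study Timeframe, Subjects, Data Collection, Methods and Procedures, Source of Materials, Protection Against Risks and the Data and Safety Monitoring Plan contain no call, return visit, records check or adverse event window after the examination. The Subjects section's two CM measurements per woman do not imply a second visit, because Methods and Procedures places the repeat measurements before the probe is removed. Source of Materials says that no additional clinical tests are ordered.

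**2. Inputs.** N = 10 (Sample Size). The plan gives no event rate, no reporting probability and no figure to reproduce, so the following are assumptions:
- p, the delayed-harm rate per woman: 0.1%, as a value consistent with the plan's wording on rarity; 1% and 2% for illustration only.
- r, the probability that a harm becomes known unprompted: 50%, range 25% to 75%.
- s, the share of otherwise unreported harms that a call finds: 80%, range 60% to 90%.
- Events are independent between women.

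**3. Chance that a harm occurs and none becomes known.** The formula is (1 − pr)^10 − (1 − p)^10. With a call, r is replaced by k = 1 − (1 − r)(1 − s). At r = 0.50 and s = 0.80, k = 1 − 0.50 × 0.20 = 0.90.

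For p = 0.001 and r = 0.50: 0.9995^10 − 0.999^10 = 0.9950 − 0.9900 = 0.0050. With the call: 0.9991^10 − 0.999^10 = 0.0010.

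| p | r = 0.25 | r = 0.50 | r = 0.75 | r = 0.50 plus call |
|---|---|---|---|---|
| 0.001 | 0.0075 | 0.0050 | 0.0025 | 0.0010 |
| 0.01 (illustrative) | 0.0709 | 0.0467 | 0.0231 | 0.0092 |
| 0.02 (illustrative) | 0.1340 | 0.0873 | 0.0427 | 0.0168 |

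**4. What no known harm in ten women supports.** The one-sided 95% upper limit for the rate of known harms is 1 − 0.05^(1/10) = 0.259. Dividing by the share that becomes known gives the limit for the true rate:
- every harm known: 25.9%
- r = 0.75: 0.259 / 0.75 = 34.5%
- r = 0.50: 0.259 / 0.50 = 51.8%
- r = 0.25: 0.259 / 0.25 exceeds 1, so there is no limit
- r = 0.50 plus a call with s = 0.80 (k = 0.90): 28.8%; with s = 0.60 (k = 0.80): 32.4%; with s = 0.90 (k = 0.95): 27.2%

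**5. Calendar.** December 1, 2016 to February 28, 2017 is 31 + 31 + 28 = 90 days. A call 7 days after an examination on day 83 (February 21) falls on day 90, which leaves no later day for a second attempt.

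**The case against.** The best reply is that silence in Data Collection and Methods and Procedures proves little. Data Collection is not a full list: it omits the palpation score, the log and the adverse event record, all of which appear elsewhere. Methods and Procedures describes only the examination, so it naturally ends there. Follow-up instructions would more likely sit in the consent form, the CRF or the written monitoring procedures, none of which can be seen. This stands, and it limits the point to what is visible. It does not remove the point, because the Data and Safety Monitoring Plan is visible and describes reporting without any contact with the woman.

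A reader might infer that safety collection stops at the visit, or that a late infection could not be recorded. The documents do not support that. The log and the adverse event reporting are open-ended, and the women are patients of the clinic, so one who returns with a problem could be logged. What is not visible is active asking.

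The size is also fairly challenged. At 0.1% the call gains about 0.4 percentage points (0.5% − 0.1%). The 1% and 2% rows have no basis in the plan, and the contrast between 51.8% and 28.8% follows directly from the assumed reporting shares. That stands too.

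Nor does the move to pregnant women rest on this end point alone: the plan also commits to bench, software and electrical safety testing, a formal device risk analysis and the federal protections for pregnant women. Miscarriage and preterm delivery cannot be observed in non-pregnant women under any follow-up.

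**Conclusion.** The point holds as a cheap improvement to consider, with medium confidence. No active follow-up is visible in a study whose first objective is risk assessment, so delayed harms are left to passive reporting before the examination is judged safe. At a rate consistent with the plan's own description (0.1%, assumed) and 50% unprompted reporting, a call that finds 80% of the remainder lowers the chance of a missed harm from about 0.5% to 0.1%.

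It would be wrong to infer that the call makes ten women enough to establish safety, or that the plan's silence shows the device to be unsafe. Even complete ascertainment leaves rates below about 26% unexcluded. The call only brings the result close to what ten women can show. The conclusion would change if the unseen consent form, CRF or monitoring procedures already schedule a contact.

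**What to change.** Add to the Data and Safety Monitoring Plan, Data Collection and the CRF: the existing study coordinator telephones each woman about 7 days after the examination and asks about fever, unusual discharge, bleeding other than expected menstruation, pain and any treatment received. Seriousness and relation are judged as the plan already requires. A woman not reached after two attempts is recorded as not reached. The 7 days is a proposal made here, not a figure from the documents.

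Add to Study End Points: safety is judged on events through this contact, and the number of women reached is reported. This gives the end point a time window but no threshold, so it remains a judgement.

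Schedule the last examination several days before February 21, 2017, or let the last calls run slightly past February 28, so that a second attempt is possible.

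The cost is ten short calls, one CRF page and one IRB amendment, with no extra patients, visits or examinations. Some symptoms will be hard to attribute, since menstruation, the preceding manual examination and the speculum can each produce them and there is no control group. Some women may not be reached.
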